8.4.3 Overdose

8.4.3.1 Durvalumab

Use of durvalumab in doses in excess of that specified in the protocol is considered to be an overdose. There is currently no specific treatment in the event of overdose of durvalumab, and possible symptoms of overdose are not established.

- An overdose with associated AEs is recorded as the AE diagnosis/symptoms on the relevant AE modules in the CRF and on the Overdose CRF module.
- An overdose without associated symptoms is only reported on the Overdose CRF module

If an overdose on an AstraZeneca study drug occurs in the course of the study, then the Investigator or other site personnel inform appropriate AstraZeneca representatives immediately, or **no later than 24 hours** of when he or she becomes aware of it.

The designated AstraZeneca representative works with the Investigator to ensure that all relevant information is provided to the AstraZeneca Patient Safety data entry site.

For overdoses associated with a SAE, the standard reporting timelines apply, see Section 8.3.2. For other overdoses, reporting must occur within 30 days.

8.4.3.2 EP treatment

Use of etoposide or platinum in doses in excess of that specified in the protocol is considered to be an overdose. Please refer to the local prescribing information for treatment of cases of overdose. If any overdose is associated with an AE or SAE please record the AE/SAE diagnosis or symptoms in the relevant AE modules of the eCRF.

8.4.4 Medication error

If a medication error occurs in the course of the study, then the Investigator or other site personnel informs the appropriate AstraZeneca representatives within 1 day (ie, immediately but no later than **24 hours** of when he or she becomes aware of it).

The designated AstraZeneca representative works with the Investigator to ensure that all relevant information is completed within 1 (Initial Fatal/Life-Threatening or follow up Fatal/Life-Threatening) or 5 (other serious initial and follow up) calendar days if there is an SAE associated with the medication error (see Section 8.3.2) and within 30 days for all other medication errors.

The definition of a Medication Error can be found in Appendix B.

8.4.5 Management of IP-related toxicities

The following general guidance should be followed for management of toxicities.

- Treat each of the toxicities with maximum supportive care (including holding the agent suspected of causing the toxicity if required).

- If the symptoms promptly resolve with supportive care, consideration should be given to continuing the same dose of the assigned IP along with appropriate continuing supportive care. If medically appropriate, dose modifications are permitted
- All dose modifications should be documented with clear reasoning and documentation of the approach taken.
- In the event that durvalumab is temporarily discontinued or delayed as part of the toxicity management guidance, EP should still be administered as scheduled; every effort should be made to ensure patients receive at least 4 cycles of EP in the study, if conditions allow.
- In the event that EP is delayed, durvalumab should also be delayed and to be resumed as soon as feasible. Every effort should be made to ensure patients receive at least 4 cycles of EP, if conditions allow.

All toxicities will be graded according to NCI CTCAE, Version 5.0.

8.4.5.1 Specific toxicity management and dose modification information – Durvalumab

Comprehensive toxicity management guidelines (TMG) have been developed to assist investigators with the recognition and management of toxicities associated with the use of the immune-checkpoint inhibitor durvalumab [Medi4736] (PD-L1 inhibitor). Additionally, these guidelines are applicable when durvalumab is used alone or in combination and is administered concurrently or sequentially with other anti-cancer drugs (i.e. antineoplastic chemotherapy, targeted agents), as part of a protocol specific treatment regimen.

The TMGs provide information for the management of immune-mediated reactions, infusion-related reactions, and non-immune mediated reactions that may be observed with checkpoint inhibitor monotherapy or combination checkpoint inhibitor regimens, with specific instructions for dose modifications (including discontinuations) and treatment interventions. Investigators are advised however to use local practice guidelines and consult local references for the management of toxicities observed with other cancer treatment (platinum and/or etoposide). The most current version of the TMGs entitled “Dosing Modification and Toxicity Management Guidelines for Immune-Mediated, Infusion-Related, and Non-Immune Mediated Reactions (MEDI4736) Monotherapy or Combination Therapy with Tremelimumab or Tremelimumab Monotherapy” is provided to the investigative site as an Annex document and is maintained within the Site Master File. In addition, a version of the current Dosing Modification and Toxicity Management Guidelines is available through the following link: <https://tmg.azirae.com>. Please contact the clinical study associate for information on how to gain access to this website.

Patients should be thoroughly evaluated and appropriate efforts should be made to rule out neoplastic, infectious, metabolic, toxin, or other etiologic causes of the imAE. Serologic, immunologic, and histologic (biopsy) data, as appropriate, should be used to support an imAE diagnosis. In the absence of a clear alternative etiology, events should be considered potentially immune related. In addition, there are certain circumstances in which durvalumab should be

permanently discontinued (see Section 7.1 of this protocol and the Dosing Modification and Toxicity Management Guidelines). Following the first dose of IP, subsequent administration of durvalumab can be modified based on toxicities observed as described in the Dosing Modification and Toxicity Management Guidelines. These guidelines have been prepared by the Sponsor to assist the Investigator in the exercise of his/her clinical judgment in treating these types of toxicities. These guidelines apply to AEs considered causally related to durvalumab by the reporting Investigator.

Dose reductions are not permitted. In case of doubt, the Investigator should consult with the Study Physician.

8.4.5.2 Specific toxicity management and dose modification information – EP treatment

Chemotherapies are associated with a number of unwanted effects. Investigators should follow local standard clinical practice regarding dose modifications, including delays and reductions, for management of etoposide- and platinum-related toxicity. For specific information regarding the individual agent used in this study, please refer to the local prescribing information for the relevant agent.

In the event of unfavorable tolerability, patients can switch between cisplatin and carboplatin therapy at any point on study (assuming eligibility for the switched therapy is met).

In the event that an AE can reasonably be attributed to EP, dose adjustment of EP should be attempted before modifying the administration of durvalumab.

In the event that EP is delayed, durvalumab should also be delayed and to be resumed as soon as feasible. Every effort should be made to ensure patients receive at least 4 cycles of EP, if conditions allow.

8.5 Pharmacokinetics

Pharmacokinetics parameters are not evaluated in this study.

8.6 Pharmacodynamics

Pharmacodynamic parameters are not evaluated in this study.

8.7 Genetics

Genetic testing is not evaluated in this study.

8.8 Biomarkers

The patient may give specific consent for sample collection for the biomarker analyses. The use of donated biological samples will be as described here (also see Table 11).

- Archival tissue samples will be obtained from all screened patients, if available (see Appendix J).

- Blood samples will be performed [REDACTED]
- Additional Blood samples will be performed [REDACTED]
- Fresh tissue sample will be obtained [REDACTED]

Details for collection, volumes, storage, and shipment of biologic samples are presented in a separate Laboratory Manual.

All samples collected for biomarker analyses will be stored at the study site or a reference laboratory, and may be used for subsequent research relevant to evaluating biological and/or clinical response to immunotherapy as described in the exploratory analyses section.

The results may be pooled with biomarker data from other durvalumab studies to evaluate biological responses across indications and to compare results in monotherapy versus combination settings.

8.8.1 Exploratory biomarkers

Blood and tumor samples for exploratory biomarker analyses will be obtained according to the schedules presented in the SoAs. Tissue samples will be collected from all screened patients in this study, if available, as specified in Section 8.8.1.1.

Details for collection, volumes, storage, and shipment of biologic samples are presented in a separate Laboratory Manual.

The exploratory biomarker plan is described by sample type below.

8.8.1.1 Collection of tumor samples for exploratory tumor biomarkers

Tumor sample requirements:

- Provision of a tumor tissue [REDACTED] Refer to the Laboratory Manual for details.

At the screening visit, a tumor sample (formalin-fixed paraffin-embedded) will be obtained from all patients. The provision of tumor tissue sample is mandatory for the patients and requires a patient consent. If a tumor block exists and there is sufficient quantity to allow for biomarker analysis, then the tumor tissue block should be shipped to the central laboratory. If a tissue block is unavailable, unstained slides from the tissue block should be provided.

See the Laboratory Manual for further details of requirements including sample quality control and shipping.

[REDACTED]

[REDACTED]

[REDACTED]

[REDACTED]

Table 11: Biomarker analysis

Sample	Biomarker
[REDACTED]	[REDACTED]

8.8.2 Management of biomarker data

The biomarker data will have unknown clinical significance. AstraZeneca will not provide biomarker research results to patients, their family members, any insurance company, an

employer, clinical study Investigator, general physician, or any other third party, unless required to do so by law. The patient's samples will not be used for any purpose other than those described in the study protocol and its appendices.

Individual patients will not be identified in any report or publication resulting from this work. The data and results of this research may be reviewed with collaborators and published, but neither the patient's name nor any other personal identifiers will appear in any publication or report.

8.8.3 Storage, re-use and destruction of biomarker samples

Samples will be stored for a maximum of 15 years from the end of study, after which they will be destroyed. Summaries and analyses for exploratory biomarkers will be documented in a separate analysis plan and will be reported outside the CSR in a separate report. The results of this biomarker research may be pooled with biomarker data from other studies involving durvalumab to generate hypotheses to be tested in future research.

8.8.4 Labeling and shipment of biological samples

The Principal Investigator will ensure that samples are labeled and shipped in accordance with the Laboratory Manual and the Biological Substance, Category B, Regulations (materials containing or suspected to contain infectious substances that do not meet Category A criteria); see Appendix C – IATA 6.2 Guidance Document.”

Any samples identified as Infectious Category A materials will not be shipped, and no further samples will be taken from the involved patients unless agreed upon with AstraZeneca and appropriate labeling, shipment, and containment provisions are approved.

8.8.5 Chain of custody of biological samples

A full chain of custody will be maintained for all samples throughout their life cycle.

The Principal Investigator at each center will keep full traceability of collected biological samples from the patients while in storage at the center until shipment or disposal (where appropriate) and will keep documentation of receipt of arrival.

The sample receiver will keep full traceability of the samples while in storage and during use until used or disposed of or until further shipment and will keep documentation of receipt of arrival.

AstraZeneca will keep oversight of the entire life cycle through internal procedures, monitoring of study sites, and auditing of external laboratory providers.

8.8.6 Withdrawal of informed consent for donated biological samples

If a patient withdraws consent to the use of donated biological samples, the samples will be disposed of or destroyed and the action documented. If samples have already been analyzed, AstraZeneca is not obliged to destroy the results of this research.

The Principal Investigator will:

- Ensure that AstraZeneca is immediately notified of the patients' withdrawal of informed consent to the use of donated samples
- Ensure that biological samples from that patient, if stored at the study site, are immediately identified, disposed of or destroyed and the action documented
- Ensure that the organization(s) holding the samples is/are immediately informed about the withdrawn consent and that samples are disposed of or destroyed, the action is documented, and the signed document is returned to the study site
- Ensure that the patient and AstraZeneca are informed about the sample disposal

8.9 Medical Resource Utilization and Health Economics

For the purposes of economic evaluation, it is necessary to capture health care resource use related to the treatment and the underlying disease. Within the study, the following will be captured:

- Number and length of hospitalizations.
- Number of visits to oncology service.
- Number of emergency visits.
- Number of outpatient visits.
- Number of imaging tests.
- Number of biopsy-related procedures.
- Treatment name, dose, duration, number of cycles.

The above resource use data will mainly come from the patient's medical record and will be captured in the eCRF.

The assessment of health economic resource use data will provide important information for payers and will be used within economic evaluations of durvalumab.

Frequency and estimates of resource use, including length of stay and number of hospital admissions, will be derived from the health resource use information.

9. STATISTICAL CONSIDERATIONS

The primary aim of the study is to describe safety profile of durvalumab in combination with platinum–etoposide as first-line treatment for patients with ES-SCLC and also as monotherapy maintenance treatment.

9.1 Statistical hypotheses

There is no formal hypotheses in this study.

9.2 Sample size determination

This is a safety study, and given the real-world setting, there is no formal predefined statistical hypothesis and no formal sample size calculation will be done.

A convenience sample size of approximately 85 patients was estimated based on the expected accrual potential during 6 months in 30 sites, although the recruitment duration may be reduced or extended, until P&R approval of durvalumab in Spain for ES-SCLC based on CASPIAN results. Therefore the number of patients recruited could be higher than 85 patients. A maximum of 30% of recruited patients will have ECOG performance status of 2 at baseline.

Assuming a sample size up to 85 and a 70% incidence of AE of CTCAE grade ≥ 3 , the estimated precision will be no wider than 10% based on exact method (Clopper-Pearson). In addition, assuming a 20% incidence of imAE, the estimated precision will be no wider than 9% using the same method. An illustration of the precision around the varying incidences of AE for the patients enrolled is provided in Table 12.

Table 11. Precision around varying incidence of AE

Precision of estimates of G3+ or imAE for varying Sample Sizes using Exact Binomial 95% CI				
Sample size	True rate of Grade 3+ AE or imAE (%) and 95% CI			
	20%	25%	60%	70%
85	$\pm 9.0\%$ 12.1-30.1	$\pm 9.7\%$ 16-35.3	10.9% 48.8-70.5	$\pm 10.0\%$ 59.7-80.0

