2.3.2.2 Durvalumab + chemotherapy

The safety and tolerability of the combination of durvalumab plus chemotherapy was evaluated in two early studies evaluating different chemotherapy regimens in patients with solid tumors: AZ study D419SC00001 and CCTG study NCT02537418. In general, the combination of durvalumab plus tremelimumab with chemotherapy appeared tolerable and manageable. On all dose levels, dose delays of durvalumab were mostly for administrative reasons/patient request and neutropenia related to chemotherapy.

In the randomized phase III CASPIAN study, durvalumab + EP was well tolerated with a manageable safety profile as first line treatment for ES-SCLC. The safety profile was consistent with the known profile of all the agents and no new safety signals were identified (Paz-Ares 2019). In summary, regardless of causality, rates of AE of any grade (98.1% vs 97.0%), grade 3 or 4 AE (61.5% vs 62.4%), serious AEs (30.9% vs 36.1%), and those leading to discontinuation (9.4% vs 9.4%) were similar between durvalumab + EP vs EP alone. Adverse events of any cause leading to death occurred in 13 (5%) and 15 (6%) patients. The most common adverse events were haematological toxicities. Immune-mediated adverse events, defined as an event that is associated with drug exposure and consistent with an immune-mediated mechanism of action, where there is no clear alternate aetiology and the event required treatment with systemic corticosteroids or other immunosuppressants and/or, for specific endocrine events, endocrine therapy, were reported by 19.6% of patients treated with durvalumab + EP compared to 2.6% of patients treated with EP alone. The majority of immune-mediated AEs were low grade and thyroid related, consistent with the known safety profile of durvalumab.

External clinical data also supports these findings. In the randomized Phase III study IMpower133 demonstrated that the safety profile of atezolizumab combined with etoposide plus carboplatin was consistent with the previously reported safety profile of the individual agents, with no new findings observed (Horn 2018).

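### The exact-CI precision in Protocol 9.2 is narrowly missed with 85 patients at 70% incidence, and tying it to at most 85 patients reverses the bound for both primary endpoints.

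*Protocol*

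**What the plan says.** Protocol 9.2 (Sample size determination) opens its precision statement with "Assuming a sample size up to 85 and a 70% incidence of AE" of CTCAE grade ≥3, and concludes that "the estimated precision will be no wider than 10% based on exact method (Clopper-Pearson" is the method. It then adds, for the second primary endpoint: "assuming a 20% incidence of imAE, the estimated precision will be no wider than 9% using the same method".

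The table that follows is headed as "using Exact Binomial 95% CI". The text calls it Table 12 and the caption calls it Table 11. It has a single row, for 85 patients, with these cells:

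- 20%: ±9.0%, 12.1-30.1
- 25%: ±9.7%, 16-35.3
- 60%: "10.9% 48.8-70.5"
- 70%: ±10.0%, 59.7-80.0

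The same section calls the 85 a convenience sample based on expected accrual, states that "no formal sample size calculation will be done", and lets the recruitment period be shortened or lengthened. The one consequence it draws for the total is that "the number of patients recruited could be higher than 85 patients". SAP 2.2 repeats the convenience sample without any precision figure.

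**The concern.** Two things look wrong. First, half of the printed interval at 70% is more than the ±10.0% printed beside it. Second, a ceiling on interval width is attached to a ceiling on sample size. Interval width falls as the sample grows, so the value at 85 is the best that a sample of at most 85 can deliver at a given incidence, not the worst.

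At stake is the accuracy of the plan's only statement of how precisely the two primary incidences will be estimated. If recruitment ended early, the sentences as worded would still promise 10% and 9%. The analysed number can also fall below the number enrolled, because Protocol 9.3.1 leaves out patients who never received study treatment.

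**Working it through.** **Inputs.** From Protocol 9.2: n = 85, incidences of 70% and 20%, and two-sided exact 95% (Clopper-Pearson) limits. The values n = 80 and n = 60 are illustrative assumptions; the documents name no reduced sample size.

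**Formula.** For x events in n patients:

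- L = 2.5% quantile of Beta(x, n − x + 1)
- U = 97.5% quantile of Beta(x + 1, n − x)
- half-width h = (U − L)/2

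**Step 1: reproduce the printed table (n = 85).**

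| Incidence | x | Exact interval | h | Half of printed interval | Printed ± |
|---|---|---|---|---|---|
| 20% | 17 | 12.10-30.08 | 8.99 | (30.1 − 12.1)/2 = 9.0 | 9.0 |
| 25% | 21 | 15.99-35.25 | 9.63 | (35.3 − 16)/2 = 9.65 | 9.7 |
| 60% | 51 | 48.80-70.48 | 10.84 | (70.5 − 48.8)/2 = 10.85 | 10.9 |
| 70% | 60 | 59.71-79.98 | 10.13 | (80.0 − 59.7)/2 = 10.15 | 10.0 |

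All four printed intervals reproduce. Half of the printed interval also gives the first three ± values, allowing for rounding of the limits. Only the 70% cell does not follow.

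**Step 2: other readings at 70%.** Since 0.70 × 85 = 59.5, the count is either 59 or 60.

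- 59/85: 58.47-78.95, h = 10.24
- 60/85: h = 10.13
- non-integer count 59.5: h = 10.19
- expected half-width over Binomial(85, 0.7): 10.12

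All exceed 10. A value of 10.0 or less comes only from the upper arm of the printed interval measured from 70% (80.0 − 70 = 10.0), or from a Wald interval: 1.96 × √(0.7 × 0.3/85) = 9.74 points. Wald is not the method named.

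**Step 3: sample size at which 10 points is met.**

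- n = 88: 61/88 gives 10.07 and 62/88 gives 9.97, so the answer depends on how the count is rounded.
- n = 89: 62/89 gives 9.98 and 63/89 gives 9.88, so both neighbouring counts pass.

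About 89 patients are needed, 4 more than 85.

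**Step 4: direction of the bound.**

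| n | 70%: count, h | 20%: count, h |
|---|---|---|
| 85 | 59-60, 10.1-10.2 | 17, 8.99 |
| 80 | 56, 10.51 | 16, 9.28 |
| 60 | 42, 12.18 | 12, 10.77 |

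The 9% claim holds at 85 and fails at 80. The 10% claim fails at all three sizes.

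**Step 5: ceiling over all incidences at n = 85.** The widest interval is at 42/85 or 43/85, with h = 11.05. A statement of at most 11.1 points is therefore safe.

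**The case against.** The strongest reply is that this is rounding. The sentences speak in whole percents, and 10.1 or 10.2 rounds to 10. The correct limits, 59.7-80.0, are printed in the same section, so a careful reader already has the true precision. This stands as a comment on size. It does not rescue a cell printed to one decimal as ±10.0%, or a strict upper limit, and it does not touch the reversed bound.

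A second reply is that Protocol 9.2 mentions only a sample larger than 85 as the result of flexible recruitment. That is so, and the smaller sizes above are illustrations. But the section expressly allows recruitment to be reduced, and the wording at issue itself covers every size up to 85.

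Two stronger readings are tempting, and the documents support neither.

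- A reader might infer that the sample size loses its justification. Protocol 9.2 rests the 85 on accrual potential, and 9.1 states no hypothesis. The precision table is only an illustration.
- A reader might infer that 70% was chosen to flatter the precision, since Protocol 2.3.2.2 reports "grade 3 or 4 AE (61.5% vs 62.4"% for the earlier phase III trial. That figure covers grades 3 and 4, while the endpoint here is grade ≥3 and so includes grade 5. The two are not like for like. The 10% sentence is also explicitly conditional on 70%, and the table already discloses the wider value at 60%.

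**Conclusion.** The point holds, at minor severity. With the method the protocol names, 85 patients give a half-width of 10.1 to 10.2 points at 70%, so the stated 10% is missed by 0.1 to 0.2 points. The 9% at 20% is met at 85 but at no appreciably smaller sample. Both sentences are wrong as bounds for samples of up to 85, and that does not depend on rounding. The size of the resulting overstatement depends on the number treated: about half a point at 70% with 80 patients (10.5 against 10) and about two points with 60 (12.2 against 10).

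This takes precision to mean half the width of the two-sided exact interval, which is the meaning that reproduces the table's other three cells. No estimate, test or stopping decision in the plan depends on the figure.

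**What to change.** Replace the two precision sentences in Protocol 9.2 with, for example:

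> With 85 treated patients the exact 95% CI half-width is about 10.1-10.2 points at 70% (59.7-80.0 for 60/85), 9.0 points at 20% (12.1-30.1 for 17/85) and at most 11.1 points at any incidence; with fewer patients it is wider (for example, 12.2 at 70% and 10.8 at 20% with n=60).

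Change the ±10.0% cell to ±10.1%, the half-width from the unrounded limits for 60/85. The other cells can stand. Merely rewording the condition to a minimum of 85 would not be enough, because the 10% is still exceeded at 85.

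The cost is a short passage of text and one table cell, with a slightly less favourable figure. The design, data collection and analysis do not change, and SAP 2.2 needs no correction because it quotes no precision.
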